7.1.5.3 Post-Treatment

- Post-treatment Follow-up Visits for Subjects Who Complete the Study or Who Discontinue Treatment but Do Not Withdraw Consent***

The last dose of MK-8962 is scheduled to be self-administered or administered by the subject's legal guardian (or someone designated by the legal guardian who has been appropriately trained) on Week 62. The subject will continue twice-weekly hCG injections with the last two doses administered in Week 64. A post-treatment follow-up visit is to be scheduled at least 21 days (but no more than 45 days) after the last dose of MK-8962, and at least 7 days after the last dose of hCG, whether the subject completed the trial or discontinued from the trial treatment prematurely. Follow-up blood samples will be

collected for assessment of anti-MK-8962 antibodies and endocrine parameters. AEs and concomitant medication will also be assessed. For subjects wishing to continue on post-trial gonadotropin treatment, such treatment should not be started until after blood sample collection at this visit.

For subjects who discontinue treatment but do not withdraw consent, after the discontinuation visits and post-treatment follow-up visit, they should:

1. Return to the clinic for key visits (V9/Week 12, V12/Week 36 and/or V15/Week 64 as applicable) to have the following procedures performed: focus physical examination, vital signs, weight and height, Tanner staging, testicular ultrasound, laboratory assessment of endocrine parameters, and safety parameters (chemistry panel and hematology), and collection of concomitant medications and adverse events. Subjects who discontinued treatment due to presence of ADA will also have serum samples collected for ADA testing at these visits. Subjects who are unable or unwilling to return to the clinic at key visits will be contacted by phone to obtain adverse events and concomitant medications.
2. Be contacted by phone in a timeframe similar to their original study visit schedule at visits that are not key visits, i.e., at V10, V11, V13, V14, up until the subject has reached the Week 64 visit. The purpose of these telephone contacts will be to assess for serious adverse events that occurred and to collect the subject's concomitant medications. The date of the telephone contact should be recorded and any serious adverse events that have occurred and concomitant medications that were used should be recorded in the eCRF.
3. In addition to the above procedures, if a subject discontinues treatment due to the presence of neutralizing ADA, he may continue to be followed every three months with repeat ADA testing after the Week 64 visit. This will continue until the ADA result becomes negative or until the subject is clinically stable (e.g., in the absence of hCG use, no clinically meaningful change in testicular volume or testosterone levels for 3 months; if hCG continues to be used, an appropriate response to hCG with stable testosterone levels) for up to 12 months after treatment discontinuation, whichever comes first.

Note: Study sites must make all reasonable efforts to counsel the subject to stay in the study even if they discontinued the study medication, and make all reasonable efforts to contact the subject. Subjects must be counseled regarding the importance of complete follow up, even when they are not continuing on study medication. Sites should make at least three attempts to make telephone contact. If telephone contacts are not successful, sites should make at least two attempts to reach the subject via certified letter before considering the subject as lost to follow-up.

If any adverse event requires supplemental procedures, they should be performed as medically necessary and recorded in the Procedures eCRF.

• ***Follow Up of Subjects Who Withdraw Consent Prior to Study Completion***

Subjects who withdraw consent and discontinue from the study will not be contacted for post-trial follow-up.

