5.5 Concomitant Medications/Vaccinations (Allowed & Prohibited)

Medications or vaccinations specifically prohibited in the exclusion criteria are not allowed during the ongoing trial. If there is a clinical indication for any medication or vaccination specifically prohibited during the trial, discontinuation from trial therapy or vaccination may be required. The investigator should discuss any questions regarding this with the Sponsor Clinical Director. The final decision on any supportive therapy or vaccination rests with the investigator and/or the subject's primary physician. However, the decision to continue the subject on trial therapy or vaccination schedule requires the mutual agreement of the investigator, the Sponsor and the subject.

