^b The Discontinuation (D/C) Visit is to be performed only if the subject does not complete the 64 week treatment. The D/C visit should be performed as soon as possible once the subject has prematurely stopped the study medication.

- c The post-treatment follow-up visit is to be scheduled at least 21 days (but no more than 45 days) after the last dose of MK-8962, and at least 7 days after the last dose of hCG (whether subject completed the trial or discontinued from the trial prematurely). Follow-up blood samples will be collected for assessment of anti-MK-8962 antibodies and PK for MK-8962 concentration. AEs and concomitant medication will also be assessed. For subjects wishing to continue on post-trial gonadotropin treatment, such treatment should not be started until after blood sample collection at this visit. For subjects who prematurely discontinue study medication, after the post-treatment follow-up visit, subjects who do not withdraw consent should: (1) return to the clinic for key visits (V9/Week 12, V12/Week 36 and/or V15/Week 64 as applicable) to have the following procedures performed: focus physical examination, vital signs, weight and height, Tanner staging, testicular ultrasound, laboratory assessment of endocrine parameters, and safety parameters (chemistry panel and hematology), and collection of concomitant medications and adverse events. Subjects discontinued from the treatment due to the presence of neutralizing ADAs will also have serum samples collected for ADA testing. Subjects who are unable or unwilling to return to the clinic at key visits will be contacted by phone to obtain adverse events and concomitant medications. (2) be contacted by phone in a timeframe similar to their original study visit schedule at visits that are not key visits, i.e., at V10, V11, V13, V14, up until the subject has reached Week 64 after V2, to assess for serious adverse events and concomitant medications. (3) Subjects discontinued from the treatment due to the presence of neutralizing antibodies may continue to be followed until the ADA result becomes negative or until clinically stable for up to 12 months after treatment discontinuation. Refer to Section 7.1.5.3 for further details.
- d For visits not involving PK sampling, a scheduling window of \pm 7 days is allowed.
- e No further injection of MK-8962 or hCG is administered at the Week 64 visit.

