8.5 Analysis Populations

8.5.1 Efficacy Analysis Populations

The Full Analysis Set (FAS) population will serve as the primary population for the analysis of efficacy data in this study. The FAS population consists of all randomized subjects who:

- receive at least one dose of study treatment
- have baseline and at least one post-baseline measurement of testicular volume
- have LH levels ≤ 3 IU/L during anytime of the study
- have received at least 36 weeks¹ of treatment (12 weeks of priming with MK-8962 followed by 24 weeks of combined treatment with MK-8962 and hCG) and have no more than 4 weeks from the last dose of MK-8962 when the last measurement is made

¹ This time point is based on the observations regarding changes in testicular volume in a study of males with HH pre-treated with recFSH for 4 months followed by 24 months of pulsatile GnRH therapy (equivalent of combined treatment with FSH and LH/hCG) [17].

A supportive analysis using the Completers population will be performed for the primary efficacy endpoint only if there are at least 5 completers. The Completers population comprises subjects who remained on the study treatment regimen and completed through Week 64.

Another supportive analysis using the modified Intent-to-Treat population will be performed for the primary efficacy endpoint. The modified ITT population comprises all randomized subjects who have received at least 36 weeks of treatment (12 weeks of priming with MK-8962 followed by 24 weeks of combined treatment with MK-8962 and hCG), and have baseline and at least one post-baseline measurement of testicular volume at ≥ 36 weeks of treatment.

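### The supportive modified ITT analysis can count testicular volumes reached on non-study gonadotropins as response to MK-8962

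*Combined protocol and SAP*

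**What the plan says.** **Permission to start other treatment.** Section 7.1.5.3 places the follow-up visit 21 to 45 days after the last MK-8962 dose and at least 7 days after the last hCG dose. It applies "whether the subject completed the trial or discontinued from the trial treatment prematurely". The section adds: "For subjects wishing to continue on post-trial gonadotropin treatment, such treatment should not be started until after blood sample collection at this visit". Section 6.0 footnote c has the same rule.

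**Continued endpoint visits.** Boys who stop treatment without withdrawing consent then return at Weeks 12, 36 and 64, as applicable, for procedures that include "Tanner staging, testicular ultrasound, laboratory assessment of endocrine parameters". Concomitant medications are recorded at these visits and at the telephone contacts between them.

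**Concomitant medication rule.** Section 5.5 states: "Medications or vaccinations specifically prohibited in the exclusion criteria are not allowed during the ongoing trial". Exclusion criterion 3 and Table 1 cover gonadotropins, GnRH, androgens and sex hormone preparations.

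**Analysis populations (Section 8.5.1).**
- The FAS is the primary population. It needs 36 weeks of treatment and a last measurement within 4 weeks of the last MK-8962 dose. It also needs LH at or below 3 "IU/L during anytime of the study".
- The mITT is supportive and covers the primary endpoint only. It needs 36 weeks of treatment, and subjects must "have baseline and at least one post-baseline measurement of testicular volume at" 36 or more weeks of treatment. It has no four-week window and no rule on other hormonal products.

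Section 8.6.1.1 and Table 6 give no model for the mITT.

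**The concern.** The first primary objective (Section 3.1) is the change in testicular volume after 64 weeks of MK-8962, with hCG added for the last 52 weeks. A boy who stops after Week 36, attends the follow-up visit and then starts another FSH preparation still has a Week 64 scan. Part of the growth on that scan may belong to the other product. Under the mITT as written, the scan is eligible and nothing flags it. The missing-at-random statement in Section 8.6.1.1 does not help, because a scan that was obtained is not missing.

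The mITT is the supportive analysis that can admit late stoppers outside the FAS window. If their Week 64 values reflect another product, agreement between the mITT and the FAS says less about MK-8962 than a reader would assume.

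**Working it through.** **1. The plan's own numbers (Section 8.9.1).** 10 completers at 30% discontinuation: 10 / 0.7 = 14.3, rounded up to 15 enrolled. In the other direction, 15 × 0.7 = 10.5, stated as 10. Both agree with the plan. Expected stoppers: 15 × 0.3 = 4.5, or 15 − 10 = 5.

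**2. Which stoppers matter.** A boy must stop after Week 36 to be in the mITT. He must also stop before about Week 61, so that the follow-up visit (at least 21 days, or 3 weeks, later) falls before Week 64. Assume stopping times are uniform over 64 weeks and ignore visit windows:
- share affected = (61 − 36) / 64 = 39%
- boys affected = 4.5 × 0.39 = 1.8 to 5 × 0.39 = 2.0

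So about 2 boys in an mITT of 10 + 2 = 12. This assumes that every such boy starts another gonadotropin and has the Week 64 scan.

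**3. Time on the other product.** A boy whose last dose is at Week 36 can have his follow-up visit from Week 39. This leaves at most 64 − 39 = 25 weeks on another product before the Week 64 scan.

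**4. Size of the shift.** Let k be the number of affected boys, n the mITT size, and δ the extra growth (log scale) due to the other product. The mean log change moves by (k / n) × δ. The documents give no value for δ, so a range is assumed. The starting point is 0.7, the Table 7 row with a geometric mean increase of 2.01. The last column divides the shift by the two-sided 95% half-width for n = 12 at SD 0.5: 2.20 × 0.5 / √12 = 0.318.

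| δ (assumed) | Shift, k = 2, n = 12 | Geometric mean increase | Shift / half-width |
|---|---|---|---|
| 0.1 | 0.017 | 2.05 | 0.05 |
| 0.2 | 0.033 | 2.08 | 0.10 |
| 0.4 | 0.067 | 2.15 | 0.21 |
| 0.7 | 0.117 | 2.26 | 0.37 |

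With δ = 0.7, another product would add in at most 25 weeks as much growth as that Table 7 row assumes over 64, so it is an outer bound. Over k = 1 to 5 (n = 10 + k) and the same range of δ, 2.01 becomes 2.03 to 2.54.

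**5. The primary population.** Other gonadotropins may start no earlier than day 21 after the last MK-8962 dose, and the FAS window closes at 4 weeks (day 28). The overlap is at most 28 − 21 = 7 days. The remaining problem is wording: the FAS rule does not say which scan is the last measurement. If an off-drug Week 64 scan counts, attending that visit removes the boy and his valid on-drug data. If it means the last volume analysed, he stays.

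**The case against.** **Is there really no on-drug limit?** The mITT condition refers to 36 or more weeks of treatment, which can be read as requiring a scan made on treatment. That reading is possible, but the text does not force it, and the four-week window written for the FAS is absent here.

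**Treatment policy.** Using every value regardless of later treatment is a legitimate choice. This stands, but the plan does not say that it makes this choice. Reporting both runs meets the point.

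**The conflict with Section 5.5.** That section says discontinuation of trial therapy may be required if a prohibited drug is indicated, and Section 7.1.5.3 describes the later treatment as post-trial. The conflict is therefore softer than a flat contradiction. Even so, the boys concerned are still followed in the trial to Week 64.

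**The fix may change the estimate little.** This also stands. Suppose 10 completers average 0.5 at Week 36 and 0.8 at Week 64, and 2 stoppers stand at 0.4 when they stop. A missing-at-random model with slope 1 predicts 0.8 − (0.5 − 0.4) = 0.7 for the stoppers at Week 64. The mean is (10 × 0.8 + 2 × 0.7) / 12 = 0.783, or 2.19-fold, against exp(0.8) = 2.23-fold if they reach 0.8 on another product. The gain is mainly a clear definition of what is estimated.

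**Stronger readings a reader might infer.**
- *That the primary result is contaminated.* The four-week window largely prevents this.
- *That the LH rule credits off-drug values to MK-8962, or will wrongly drop boys.* The rule belongs to the FAS and removes boys; it credits nothing. The documents do not show that other gonadotropins raise measured LH above 3 IU/L. LH and hCG are listed as separate tests (Section 7.1.3.2), and all boys in the combined phase receive hCG. The Section 8.5.1 footnote on pulsatile GnRH justifies the 36-week threshold and does not concern LH readings. The permission itself names gonadotropins only.
- *That Tanner stage, height and hormone results in the mITT are affected.* The mITT covers the primary endpoint only.

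**Conclusion.** The gap is real but limited. A Week 64 volume obtained on another gonadotropin can enter the mITT as MK-8962 response, because neither the mITT definition nor the methods section deals with it. It touches mainly a supportive analysis, and only boys who stop between about Week 36 and Week 61. Boys who stop earlier are in neither population.

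The size, about 2 of 12 boys and 2.05- to 2.26-fold in place of 2.01-fold, rests on uniform stopping times, on all such boys switching and being scanned, and on assumed values of δ. It would not by itself overturn a conclusion, but the remedy is cheap enough to be worth making.

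**What to change.** In Sections 8.5.1 and 8.6.1:

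1. State that testicular volumes obtained after the first dose of any non-study gonadotropin, GnRH or androgen are not used in the main mITT analysis.
2. Name the mITT model and add it to Table 6.
3. Report how many boys and scans this affects, and give one mITT run that keeps them.
4. Define the last measurement in the FAS rule as the last volume used in the analysis. Volumes beyond the four-week window are then left out, and attending an off-drug visit does not cost a boy his on-drug data. With such boys retained, state the cut-off for the secondary FAS summaries too.
5. As a precaution only, limit the LH rule to values taken before any non-study gonadotropin, GnRH or androgen.

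Sections 5.5, 6.0 (footnote c) and 7.1.5.3 must be reconciled on whether such treatment is permitted in boys still followed to Week 64. That decision belongs to the sponsor and investigators.

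**Cost.** Mostly analysis wording, plus a small protocol edit. The medication data are already collected. A boy treated for 36 weeks is scheduled for an on-drug Week 36 scan, so he will generally stay in the mITT. A few scans leave its main run, and its confidence interval becomes slightly wider.

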7.2 Assessing and Recording Adverse Events

An adverse event is defined as any untoward medical occurrence in a patient or clinical investigation subject administered a pharmaceutical product and which does not necessarily have to have a causal relationship with this treatment. An adverse event can therefore be any unfavourable and unintended sign (including an abnormal laboratory finding, for example), symptom, or disease temporally associated with the use of a medicinal product or protocol-specified procedure, whether or not considered related to the medicinal product or protocol-specified procedure. Any worsening (i.e., any clinically significant adverse change in frequency and/or intensity) of a preexisting condition that is temporally associated with the use of the Sponsor's product, is also an adverse event.

Changes resulting from normal growth and development that do not vary significantly in frequency or severity from expected levels are not to be considered adverse events. Examples of this may include, but are not limited to, teething, typical crying in infants and children and onset of menses or menopause occurring at a physiologically appropriate time.

Sponsor's product includes any pharmaceutical product, biological product, device, diagnostic agent or protocol-specified procedure, whether investigational (including placebo or active comparator medication) or marketed, manufactured by, licensed by, provided by or distributed by the Sponsor for human use.

Adverse events may occur during clinical trials, or as prescribed in clinical practice, from overdose (whether accidental or intentional), from abuse and from withdrawal.

All adverse events that occur after the consent form is signed but before treatment allocation/randomization must be reported by the investigator if they cause the subject to be excluded from the trial, or are the result of a protocol-specified intervention, including but not limited to washout or discontinuation of usual therapy, diet, placebo treatment or a procedure. From the time of treatment allocation/randomization through the follow-up visit (i.e., at least 21 days following last dose of MK-8962) following cessation of treatment, all adverse events must be reported by the investigator. Such events will be recorded at each examination on the Adverse Event case report forms/worksheets. The reporting timeframe for adverse events meeting any serious criteria is described in section 7.2.2.1. The investigator will make every attempt to follow all subjects with non-serious adverse events for outcome.

Electronic reporting procedures can be found in the EDC data entry guidelines. Paper reporting procedures can be found in the Investigator Trial File Binder (or equivalent).

7.2.1 Definition of an Overdose for This Protocol and Reporting of Overdose to the Sponsor

In this trial, an overdose for MK-8962 is any dose exceeding the doses as prescribed by the protocol, or if two doses of MK-8962 are given less than 7 days apart. For hCG, investigators/site personnel are to consult the local approved hCG product label for guidance on the definition of overdose.

If an adverse event(s) is associated with ("results from") the overdose of Sponsor's product or vaccine, the adverse event(s) is reported as a non-serious adverse event, unless other seriousness criteria are met.

If a dose of Sponsor's product or vaccine meeting the protocol definition of overdose is taken without any associated clinical symptoms or abnormal laboratory results, the overdose is reported as a non-serious adverse event, using the terminology "accidental or intentional overdose without adverse effect."

All reports of overdose with and without an adverse event must be reported by the investigator within 24 hours to the Sponsor either by electronic media or paper. Electronic reporting procedures can be found in the EDC data entry guidelines. Paper reporting procedures can be found in the Investigator Trial File Binder (or equivalent).

